7.1.1. Liver Chemistry Stopping Criteria

Liver chemistry stopping and increased monitoring criteria have been designed to assure participant safety and evaluate liver event etiology.

Discontinuation of study treatment for abnormal liver tests is required when:

- a participant meets one of the conditions outlined in the Figure 2
 - OR
- when in the presence of abnormal liver chemistries not meeting protocol-specified stopping rules, the investigator believes study treatment discontinuation is in the best interest of the participant.

Figure 2 Phase I Liver Chemistry Stopping and Increased Monitoring Algorithm for Participants WITH entry criteria ALT ≤2.5xULN

Liver Safety Required Actions and Follow up Assessments Section can be found in Appendix 5.

7.1.1.1. Study treatment Restart or Rechallenge after liver stopping criteria met

If participant meets liver chemistry stopping criteria do not restart/rechallenge participant with study treatment unless:

- GSK Medical Governance approval is granted
- Ethics and/or IRB approval is obtained, if required, and
- Separate consent for intervention restart/rechallenge is signed by the participant Refer to Appendix 5 for details.

If GSK Medical Governance approval to restart/rechallenge participant with study treatment **is not granted**, then participant must permanently discontinue study treatment and may continue in the study for protocol-specified follow up assessments.

7.1.2. Allergic and Anaphylactic Reaction Stopping Criteria

All participants will be monitored carefully for evidence of allergic response. A participant that exhibits signs or symptoms of severe hypersensitivity or anaphylaxis will receive appropriate medical treatment and permanently discontinue study treatment but will continue in the study.

7.1.3. Stopping Criteria Based on Ocular Examination Findings

Belantamab mafodotin dose modifications and stopping criteria for treatment-related changes in visual acuity are detailed in Table 7, according to CTCAE criteria (Version 5.0, 2017). Participants who develop a Grade 4 event should be discussed with the GSK Medical Monitor to determine whether the participant can be allowed to continue treatment with belantamab mafodotin or whether belantamab mafodotin should be permanently discontinued. The decision will be documented in study files, together with individual assessment of risk-benefit. For details on re-start guidance (Table 7).

7.1.4. Infusion-Related Reaction Stopping Criteria

Premedication is not required prior to infusion unless deemed medically appropriate by the investigator following evaluation of IRRs. Premedication should be considered in any participant who experienced an IRR at first or any subsequent infusion with belantamab mafodotin.

Infusion related reactions should be managed by guidelines provided in Table 5. A participant that experiences a Grade 4 IRR must permanently discontinue study treatment but will continue in the study.

7.2. Participant Discontinuation/Withdrawal from the Study

A participant may withdraw from the study at any time at his/her own request, or may be withdrawn at any time at the discretion of the investigator for safety, behavioural, compliance or administrative reasons.

At the time of discontinuing from the study, if possible, an early discontinuation visit should be conducted. See SoA for data to be collected at the time of study discontinuation and follow-up and for any further evaluations that need to be completed.

If the participant withdraws consent for disclosure of future information, the sponsor may retain and continue to use any data collected before such a withdrawal of consent.

If a participant withdraws from the study, he/she may request destruction of any samples taken and not tested, and the investigator must document this in the site study records.

Withdrawn participants will not be replaced.

7.3. Lost to Follow Up

A participant will be considered lost to follow-up if he or she repeatedly fails to return for scheduled visits and is unable to be contacted by the study site.

The following actions must be taken if a participant fails to return to the clinic for a required study visit:

- The site must attempt to contact the participant and reschedule the missed visit as soon as possible and counsel the participant on the importance of maintaining the assigned visit schedule and ascertain whether or not the participant wishes to and/or should continue in the study.
- Before a participant is deemed lost to follow up, the investigator or designee must make every effort to regain contact with the participant (where possible, 3 telephone calls and, if necessary, a certified letter to the participant's last known mailing address or local equivalent methods). These contact attempts should be documented in the participant's medical record.
- Should the participant continue to be unreachable, he/she will be considered to have withdrawn from the study.

Discontinuation of specific sites or of the study as a whole are handled as part of Appendix 1.

8. STUDY ASSESSMENTS AND PROCEDURES

A signed, written informed consent form must be obtained from the participant prior to any study-specific procedures or assessments being performed. The timing of each assessment is listed in the Schedule of Activities (Table 1).

A list of clinical laboratory tests is displayed in Appendix 2.

Whenever vital signs, 12-lead electrocardiograms (ECGs) and blood draws are scheduled for the same nominal time, the assessments must occur in the following order: 12-lead ECG, vital signs, blood draws. The timing of the assessments must allow the blood draw to occur at the exact nominal time. Detailed procedures for obtaining each assessment are provided in the SRM.

- Study procedures and their timing are summarised in the SoA.
- Protocol waivers or exemptions are not allowed
- Immediate safety concerns should be discussed with the sponsor immediately upon occurrence or awareness to determine if the participant should continue or discontinue study treatment.
- Adherence to the study design requirements, including those specified in the SoA, is essential and required for study conduct.
- All screening evaluations must be completed and reviewed to confirm that potential participants meet all eligibility criteria. The investigator will maintain a screening log to record details of all participants screened and to confirm eligibility or record reasons for screening failure, as applicable.
- Procedures conducted as part of the participant's routine clinical management (e.g., blood count) and obtained before signing of ICF may be utilised for screening or

baseline purposes provided the procedure met the protocol-specified criteria and was performed within the time frame defined in the SoA.

• Visit Windows:

- Baseline disease assessments must be completed with 21 days prior to dosing start unless otherwise specified. Refer to SoA.
- Screening assessments performed within the permitted time do not need to repeated on C1D1 unless otherwise specified.
- Safety labs completed within 72 hours of first dose do not need to be repeated on C1D1.
- Pregnancy testing must be completed within 72 hours prior to first dose.
- An ECHO completed within 3 months prior to screening can be used as a screening value.
- Imaging applicable for participants with extramedullary disease must be completed within 30 days prior to first dose.
 - On study visits have a ± 3 -day window and PD follow-up visits have a ± 7 -day window.
- Repeat or unscheduled samples may be taken for safety reasons or for technical issues with the samples.

8.1. Efficacy Assessments

Standard disease assessments for RRMM will include the following assessments:

- UPEP, Urine Immunofixation, 24 hr collection for urine M-protein
- SPEP, Serum M-protein, serum immunofixation
- Calcium corrected for albumin
- IgD, IgE (only in participants with IgD or IgE myeloma)
- Serum Kappa, lambda free LC, FLC ratio
- Bone marrow aspirate at screening (in case of CR, CCI), or immunohistochemistry (IHC) to confirm sCR.
- Imaging of extramedullary disease (only in participants with extramedullary disease)
- Skeletal surveys at screening

Response evaluation will be performed according to the IMWG Uniform Response Criteria for Multiple Myeloma 2016 (Appendix 6).

Baseline serum/urine disease assessment will be completed during screening period (within 21 days prior to the first dose of study treatment) and baseline imaging within 30 days prior to the first dose of study treatment. On study serum and urine based assessments (M-protein, and FLC) will be performed every 3 weeks (at the start of each cycle). The serum and urine immunofixation will be performed as clinical indicated at the time of first achieving CR or suspected PD after CR or sCR. Details for the preparation and shipment of samples for central laboratory assessments will be provided in the SRM.

In participants with extramedullary myeloma, the disease assessments must include imaging (e.g., CT, MRI, or PET-CT scans- the same method should be used throughout the study) and physical examination (as indicated for palpable/superficial lesions).

For participants who are followed by imaging for extramedullary disease the imaging has to be performed as described in the SoA (Table 1).

All assessments on study must be performed on a calendar schedule and must not be affected by dose interruptions/delays. For post-baseline assessments, a window of ± 3 days is permitted to allow for flexible scheduling.

The confirmation of PD must be performed within 14 days, but NOT on the same day, and NOT from the same blood draw as the initial test documenting PD. The assessments will be performed during End of Treatment (EOT) follow-up Visit (Table 1) for the Schedule of Activities of anti-cancer activity.

If the last disease assessment was greater than or equal to 6 weeks prior to the participant's discontinuation from study treatment and progressive disease has not been documented, a new disease assessment must be obtained at the PD follow-up visit following discontinuation from study treatment.

8.2. Safety Assessments

Planned time points for all safety assessments are provided in the SoA.

8.2.1. Physical Examinations

At screening, on dosing days, and at end of study treatment visit a full physical examination will include assessments of the head, eyes, ears, nose, throat, skin, thyroid, lungs, cardiovascular, abdomen (liver and spleen), lymph nodes, and extremities. Height (once at screening only) and weight must also be measured and recorded.

8.2.2. Vital Signs

Vital sign measurements must include systolic and diastolic blood pressure, temperature, and heart rate. Vital signs must be measured after resting for at least 5 minutes. Vital signs must be measured more frequently if warranted by the clinical condition of the participant. On days where vital signs are measured multiple times, temperature does not need to be repeated unless clinically indicated.

8.2.2.1. First Infusion

Monitoring intervals: Vital signs must be monitored at designated time points related to drug infusion as specified in the Schedule of Activities (Section 1.3) In general, participants must also be monitored for at least 1 hour after the completion of the first infusion and may be discharged if considered clinically stable and all other study procedures have been completed.

8.2.2.2. Subsequent Infusions

Monitoring intervals: Vital signs must be monitored at designated time points related to drug infusion as specified in the Schedule of Activities (Section 1.3) Participants may be discharged after the infusion has been completed if considered clinically stable and all other study procedures have been completed.

8.2.3. Electrocardiograms

12-lead electrocardiogram (ECGs) must be obtained in triplicate at designated time points and as single assessments at other time points as specified in the Schedule of Activities (Section 1.3). The ECG machine must automatically calculate the heart rate and measure PR, QRS, QT, and corrected QT (QTc) intervals. At each assessment, a 12-lead ECG must be performed by qualified personnel at the site after the participant has at least a 5-minute rest.

The QT interval must be corrected for heart rate by Fridericia's formula (QTcF). Refer to the SRM for details regarding ECG procedures.

8.2.4. Echocardiogram

Echocardiograms (ECHOs) must be performed at baseline to assess cardiac ejection fraction for the purpose of study eligibility, as specified in the SoA. The evaluation of the echocardiographer must include an evaluation for left ventricular ejection fraction (LVEF). If an ECHO is performed on study, the results must be documented in the e-CRF.

8.2.5. Clinical Safety Laboratory Assessments

- Refer to Appendix 2 for the list of clinical laboratory tests to be performed and to the SoA for the timing and frequency.
- The investigator must review the laboratory report, document this review, and record any clinically relevant changes occurring during the study in the AE section of the CRF. The laboratory reports must be filed with the source documents. Clinically significant abnormal laboratory findings are those, which are not associated with the underlying disease, unless judged by the investigator to be more severe than expected for the participant's condition.
- All laboratory tests with values considered clinically significantly abnormal during participation in the study or within 30 days after the last dose of study treatment should be repeated until the values return to normal or baseline or are no longer considered significantly abnormal by the investigator or medical monitor.
- If such values do not return to normal/baseline within a period of time judged reasonable by the investigator, the etiology should be identified and the sponsor notified.
- All protocol-required laboratory assessments, as defined in Appendix 2, must be conducted in accordance with the laboratory manual and the SoA.

8.2.6. ECOG Performance Status

Participant performance status will be assessed at Screening, using the Eastern Cooperative Oncology Group (ECOG) scale, provided in Appendix 7.

8.2.7. Visual Function Questionnaire

The impact of potential ocular toxicity on function and health-related quality-of-life will be assessed with the use of a visual function questionnaire, the OSDI. All participants will use the Self-Administered version of the questionnaire, unless their vision prevents them from being able to complete the questionnaire on their own. Participants who are not able to complete the questionnaire on their own and require assistance must use an Interviewer Administered format. If the Interviewer Administered format is being used, it must be read to the participants verbatim, and participant responses must be recorded directly without any interpretation. For any additional assessments conducted via telephone (either during participation in the treatment period or during Follow-up), the Interviewer Administered format must be used.

The OSDI will be administered to participants in different regions based on the availability of translated versions.

8.2.7.1. The Ocular Surface Disease Index

The Ocular Surface Disease Index (OSDI) is a 12-item questionnaire designed to assess both the frequency of dry eye symptoms and their impact on vision-related functioning [Schiffman, 2000; Dougherty, 2011]. The OSDI has demonstrated good reliability, validity, sensitivity, and specificity, and can be used as a complement to other clinical and subjective measures of dry eye disease by providing a quantifiable assessment of dry eye symptom frequency and the impact of these symptoms on vision-related functioning.

8.3. Adverse Events and Serious Adverse Events

The definitions of an AE or SAE can be found in Appendix 3.

The investigator and any qualified designees are responsible for detecting, documenting, and reporting events that meet the definition of an AE or SAE and remain responsible for following up AEs that are serious, considered related to the study treatment or the study, or that caused the participant to discontinue the study treatment (see Section 6).

8.3.1. Time Period and Frequency for Collecting AE and SAE Information

- All SAEs will be collected from signing of the ICF until 70 days following discontinuation of study treatment regardless of initiation of a new cancer therapy or transfer to hospice at the time points specified in the SoA (Table 1). However, any SAEs assessed as related to study participation (e.g., study intervention, protocol-mandated procedures, invasive tests, or change in existing therapy) or related to a GSK product will be recorded from the time a participant consents to participate in the study up to and including follow up.
- All AEs will be collected from the start of treatment until 70 days following discontinuation of study treatment regardless of initiation of a new cancer therapy or transfer to hospice at the time points specified in the SoA.
- Medical occurrences that begin before the start of study treatment but after obtaining informed consent will be recorded on the Medical History/Current Medical Conditions section of the electronic case report form (eCRF) not the AE section.
- All SAEs will be recorded and reported to the sponsor or designee immediately and under no circumstance should this exceed 24 hours, as indicated in Appendix 3. The investigator will submit any updated SAE data to the sponsor within 24 hours of it being available.
- Investigators are not obligated to actively seek AEs or SAEs in former study participants. However, if the investigator learns of any SAE, including a death, at any time after a participant has been discharged from the study, and he/she considers the event to be reasonably related to the study treatment or study participation, the investigator must promptly notify the sponsor.

8.3.2. Method of Detecting AEs and SAEs

- The method of recording, evaluating, and assessing causality of AEs and SAEs and the procedures for completing and transmitting SAE reports are provided in Appendix 3.
- Care will be taken not to introduce bias when detecting AE and/or SAE. Openended and non-leading verbal questioning of the participant is the preferred method to inquire about AE occurrence.

8.3.3. Follow-up of AEs and SAEs

After the initial AE/SAE report, the investigator is required to proactively follow each participant at subsequent visits/contacts. All SAEs, non-serious AEs of special interest, will be followed until the event is resolved, stabilised, otherwise explained, or the participant is lost to follow-up (as defined in Section 7.3). Further information on follow-up procedures is given in Appendix 3.

8.3.4. Regulatory Reporting Requirements for SAEs

- Prompt notification by the investigator to the sponsor of a SAE is essential so
 that legal obligations and ethical responsibilities towards the safety of
 participants and the safety of a study treatment under clinical investigation are
 met.
- The sponsor has a legal responsibility to notify both the local regulatory authority and other regulatory agencies about the safety of a study treatment under clinical investigation. The sponsor will comply with country-specific regulatory requirements relating to safety reporting to the regulatory authority, Institutional Review Boards (IRB)/Independent Ethics Committees (IEC), and investigators.
- Investigator safety reports must be prepared for suspected unexpected serious adverse reactions (SUSAR) according to local regulatory requirements and sponsor policy and forwarded to investigators as necessary.
- An investigator who receives an investigator safety report describing a SAE or
 other specific safety information e.g., summary or listing of SAE) from the
 sponsor will review and then file it along with the Investigator's Brochure and
 will notify the IRB/IEC, if appropriate according to local requirements.

8.3.5. Pregnancy

Do not collect pregnancy information for female participants known to be pregnant during the screening phase or before exposure to study.

The need for a screening pregnancy test depends on whether a female participant is of childbearing potential or non-childbearing potential.

• Details of all pregnancies in female participants will be collected after the start of study treatment and for 8 months following last dose of belantamab mafodotin.

- Details of all pregnancies for female partners of male participants will be collected after the start of study treatment and 5 months following last dose of belantamab mafodotin.
- If a pregnancy is reported, the investigator must inform GSK within 24 hours of learning of the pregnancy and must follow the procedures outlined in Appendix 4.
- Abnormal pregnancy outcomes (e.g., spontaneous abortion, fetal death, stillbirth, congenital anomalies, and ectopic pregnancy) are considered SAE.

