	Cases of elevated aspartate aminotransferase (AST), lactic dehydrogenase (LDH) and creatine kinase (CK), and GGT alone or concomitant with no clear clinical correlate have been observed in clinical studies.	
Embryo-Fetal Toxicity	Nonclinical reproductive studies with belantamab mafodotin have not been conducted. Embryo-fetal toxicity is expected due to the cytotoxic component, cys-mcMMAF via nonspecific uptake and/or BCMA-mediated toxicity (due to reports of BCMA expression in human placental cells [Langat, 2008]).	See Contraception requirements in Section 5.1 and Appendix 4. Pregnancy testing outlined in the SoA. 1.3

Potential Risk of Clinical Significance	Summary of Data/Rationale for Risk	Mitigation Strategy	
	Use of belantamab mafodotin in pregnant women may cause fetal harm.		
Impaired Male and Female Fertility	In animal studies, belantamab mafodotin treatment has resulted in testicular toxicity and adverse effects on spermatogenesis. Reversibility of testicular toxicity is unknown at this time.	Men who may wish to father children in the future will be advised to have sperm samples frozen and stored prior to belantamab mafodotin treatment.	
	Ovarian toxicity (luteinized non-ovulatory follicles) was observed in a 3-week rat study (weekly dosing) and not observed following 12 weeks off dose. In a 13-week rat study where drug was administered once every 3 weeks, these changes were not observed.	Women of child bearing potential who may desire offspring in the future will be counselled about the option of having eggs frozen before treatment. See Contraception requirements in Section 5.1 and Appendix 4.	
	Study Procedures		
Bone marrow aspiration/biopsy	Pain, infection, bleeding may occur after the procedure	Participants will be treated according to institution's practice	
Incidental findings during image data acquisition:	During the acquisition of imaging data (e.g MRI, CT, PET, ECG), non- disease or clinically relevant abnormalities could be found by the radiographer or echocardiographer performing the exams.	Copies of all medical images that include non-disease, clinically relevant abnormalities will be shared with the site for storage	

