Male participants are eligible to participate if they agree to the following from the time of first dose of study until 6 months after the last dose of study treatment to allow for clearance of any altered sperm:

- Refrain from donating sperm PLUS either:
- Be abstinent from heterosexual intercourse as their preferred and usual lifestyle (abstinent on a long term and persistent basis) and agree to remain abstinent.

OR

- Must agree to use contraception/barrier as detailed below:
 Agree to use a male condom, even if they have undergone a successful
 vasectomy and female partner to use an additional highly effective
 contraceptive method with a failure rate of <1% per year when having sexual
 intercourse with a woman of childbearing potential who is not currently
 pregnant.
- 10. All prior treatment-related toxicities (defined by National Cancer Institute-Common Toxicity Criteria for Adverse Events (NCI-CTCAE), version 5.0 must be ≤Grade 1 at the time of enrolment except for alopecia and Grade 2 peripheral neuropathy.

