 Spermatogenesis cycle is approximately 90 days.
- Highly Effective Methods^b That Are User Dependent
- Combined (estrogen- and progestogen-containing) hormonal contraception associated with inhibition of ovulation^c
 - oral
 - intravaginal
 - transdermal
 - injectable
- Progestogen-only hormone contraception associated with inhibition of ovulation^c
 - oral
 - injectable
- Sexual abstinence
 - Note: Sexual abstinence is considered a highly effective method only if defined as refraining from
 heterosexual intercourse during the entire period of risk associated with the study treatment. The
 reliability of sexual abstinence needs to be evaluated in relation to the duration of the study and the
 preferred and usual lifestyle of the participant
- a. Contraceptive use by men or women should be consistent with local regulations regarding the use of contraceptive methods for those participating in clinical studies.
- b. Failure rate of <1% per year when used consistently and correctly. Typical use failure rates differ from those when used consistently and correctly.
- c. Male condoms must be used in addition to hormonal contraception. If locally required, in accordance with Clinical Trial Facilitation Group (CTFG) guidelines, acceptable contraceptive methods are limited to those which inhibit ovulation as the primary mode of action.

Note: Periodic abstinence (calendar, sympto-thermal, post-ovulation methods), withdrawal (coitus interruptus), spermicides only, and lactational amenorrhoea method (LAM) are not acceptable methods of contraception for this study. Male condom and female condom should not be used together (due to risk of failure with friction)

Collection of Pregnancy Information

Male participants with partners who become pregnant

• Investigator will attempt to collect pregnancy information of a female partner of a male study participant who becomes pregnant while participating in this study, and

- for 6 months following last dose of belantamab mafodotin. This applies only to male participants who receive study treatment.
- After obtaining the necessary signed informed consent from the pregnant female partner directly, the investigator will record pregnancy information on the appropriate form and submit it to GSK within 24 hours of learning of the partner's pregnancy.
- The female partner will also be followed to determine the outcome of the pregnancy. Information on the status of the mother and child will be forwarded to GSK

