- Generally, follow-up will be no longer than 6 to 8 weeks following the estimated delivery date. Any termination of the pregnancy will be reported regardless of fetal status (presence or absence of anomalies) or indication for procedure.

Female Participants who become pregnant

- Investigator will collect pregnancy information on any female participant, who becomes pregnant while participating in this study, for 4months following last dose of belantamab mafodotin.
- Information will be recorded on the appropriate form and submitted to GSK within 24 hours of learning of a participant's pregnancy.
- Participant will be followed to determine the outcome of the pregnancy. The investigator will collect follow up information on participant and neonate, which will be forwarded to GSK Generally, follow-up will not be required for longer than 6 to 8 weeks beyond the estimated delivery date.
- Any termination of pregnancy will be reported, regardless of fetal status (presence or absence of anomalies) or indication for procedure.
- While pregnancy itself is not considered to be an AE or SAE, any pregnancy complication or elective termination of a pregnancy will be reported as an AE or SAE.
- A spontaneous abortion is always considered to be an SAE and will be reported as
- Any SAE occurring as a result of a post-study pregnancy which is considered
 reasonably related to the study treatment by the investigator, will be reported to GSK
 as described in Appendix 4 While the investigator is not obligated to actively seek
 this information in former study participants, he or she may learn of an SAE through
 spontaneous reporting.

Any female participant who becomes pregnant while participating will discontinue study treatment.

11.5. Appendix 5: Liver Safety: Required Actions and Follow-up Assessments and Study treatment Rechallenge Guidelines

Phase I liver chemistry stopping and increased monitoring criteria have been designed to assure participant safety and evaluate liver event etiology.

Liver Chemistry Stopping Criteria – Liver Stopping Event				
ALT-absolute	ALT ≥5xULN			
ALT Increase	ALT ≥3xULN persists for ≥4 weeks			
Bilirubin ^{1, 2}	ALT ≥3xULN and bilirubin ≥2xULN (>35% direct bilirubin)			
INR ²	ALT ≥3xULN and INR >1.5			
Cannot Monitor	ALT ≥3xULN and cannot be monitored weekly for 4 weeks			
Symptomatic ³	ALT ≥3xULN associated with symptoms (new or worsening) believed to be related to liver injury or hypersensitivity			

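### Section 8.3.5 ends collection of partner pregnancies at 5 months after last dose where Appendix 4 says 6; for female participants the two sections say 8 and 4 months

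*Protocol*

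**What the plan says.** Two parts of the current protocol set how long pregnancies are collected after the last dose.

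- **Partners of male participants.** Section 8.3.5 has these pregnancies "collected after the start of study treatment and 5 months following last dose of belantamab mafodotin". Appendix 4 (Section 11.4) has the investigator attempt to collect them during participation and "for 6 months following last dose of belantamab mafodotin".
- **Female participants.** Section 8.3.5 has pregnancies "collected after the start of study treatment and for 8 months following last dose of belantamab mafodotin". Appendix 4 covers a female participant "who becomes pregnant while participating in this study, for 4months following last dose of belantamab mafodotin".

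The related periods are these:

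- Inclusion criterion 9 (Section 5.1) binds male participants to contraception or abstinence "until 6 months after the last dose of study treatment to allow for clearance of any altered sperm".
- Inclusion criterion 8 sets female contraception at 4 months after last dose.
- Schedule of Activities footnote 16a places a final pregnancy test at 8 months after last dose. SAP Appendix 2 repeats that footnote.

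On the reason for the male period, the risk table in Section 2.4.1 says that in animals "belantamab mafodotin treatment has resulted in testicular toxicity and adverse effects on spermatogenesis", and adds: "Reversibility of testicular toxicity is unknown at this time".

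**The concern.** Two operative instructions give different durations for the same safety data, and the protocol has no rule for choosing between them. Section 8.3.5 does refer to Appendix 4, but the reference starts "If a pregnancy is reported, the investigator must inform GSK within 24 hours" and is about what to do next. It does not lengthen the period in which pregnancies are looked for. Footnote 16, which concerns women of childbearing potential, sends the site to both sections.

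For partners the shorter figure is on the unsafe side. Male contraception runs to 6 months because sperm may still be altered until then, so a conception in the sixth month is one the sponsor would want to know about. Section 8.3.5 read alone leaves that month out.

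For female participants Section 8.3.5 is the longer text, so nothing in the 4-month contraception period is missed. What is left is a loose end: a pregnancy that begins after month 4 and is first found at the 8-month test is collected under Section 8.3.5 and falls outside Appendix 4.

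**Working it through.** The plan has no figure of its own to reproduce here. The check is a side-by-side reading plus month-to-day arithmetic.

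| After last dose | Section 8.3.5 | Appendix 4 | Contraception (Section 5.1) | Final test (footnote 16a) |
|---|---|---|---|---|
| Partners of male participants | 5 months | 6 months | 6 months | none |
| Female participants | 8 months | 4 months | 4 months | 8 months |

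Appendix 4 agrees with the contraception periods in both rows. Section 8.3.5 agrees only with the test date in footnote 16a.

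**Conversion.** 1 month = 365.25 / 12 = 30.44 days, so 4 months = 121.8 days, 5 months = 152.2, 6 months = 182.6 and 8 months = 243.5.

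**Partner gap.** 182.6 − 152.2 = 30.4 days, from about day 152 to day 183. As a share of the post-dose male contraception period: 30.4 / 182.6 = 16.7%. If the site applies Appendix 4, the gap is 0 days.

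**People exposed to the gap.** The rationale for Amendment 3 mentions two ongoing participants and does not give their sex.

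- Lower bound: 0, if neither is a man with a partner of childbearing potential.
- Upper bound: 2 × 30.4 = 60.9 participant-days, if both are.

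These bounds cover only those two. Participants who had stopped but were still within 6 months of last dose would add to them, and the documents do not count such participants.

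**Female participants.** The collection periods differ by 243.5 − 121.8 = about 122 days. Contraception time left uncovered is max(0, 4 − 4) = 0 months under Appendix 4 and max(0, 4 − 8) = 0 months under Section 8.3.5.

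**Other routes by which a missed pregnancy could surface.** Section 8.3.1 requires a related SAE learned of after discharge to be reported, but it does not oblige investigators to look for one. Under Appendix 4 a pregnancy is not in itself an adverse event, so an uncomplicated partner pregnancy would not come in this way. The Appendix 4 bullet on SAEs from post-study pregnancies stands under the heading for female participants.

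**Effect on the analysis.** SAP Section 8.6 puts pregnancies in narratives and plans no table or listing. No endpoint or dose decision depends on either period.

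**The case against.** The best reply is that both texts can be obeyed together. Each sets a duty to collect, and neither forbids collecting for longer. A site that honours both collects for 8 months in women and 6 months in partners and loses nothing. The intended partner figure is also easy to see, since Appendix 4 and criterion 9 agree on 6 months; Section 8.3.5 looks like a missed edit. This is right about intent. It does not remove the problem, because no text tells the site to take the longer period, and a site that stops at 5 months has followed Section 8.3.5 to the letter.

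The second reply is that almost nothing would be missed. Unless abstinent, criterion 9 requires a condom plus a partner method failing in under 1% of users a year. If that is kept to, and both ongoing participants are men with partners of childbearing potential, the expected number of pregnancies in the gap is below 2 × 0.01 × 30.4 / 365.25 = about 0.002. With all 12 planned evaluable participants in that position it is about 0.01. Partner collection is also best-effort even inside the period, since Appendix 4 requires the partner's own consent. All of this stands, as does the absence of any effect on the analysis. It limits the severity to minor; it is no reason to keep two contradictory safety instructions.

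The third reply is that the female mismatch does no harm and could equally be settled at 4 months. No contraception time is uncovered, and 4 months would be consistent with criterion 8. But that choice also requires changing footnote 16a and its copy in the SAP.

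**Conclusion.** The inconsistency is real, and the severity is minor. Section 8.3.5 and Appendix 4 disagree on both collection periods: 5 against 6 months for partners, and 8 against 4 months for female participants.

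The partner figure in Section 8.3.5 is wrong as written, because it ends before the male contraception period does. The size is one month, under the assumption that a site uses Section 8.3.5 alone. The number of participants affected cannot be fixed more closely than 0 to 2 among those recorded as ongoing, plus an unknown number of recent stoppers. The female difference is one of consistency only. Confidence is high, since all four periods are read directly from current text.

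**What to change.** 1. In Section 8.3.5, change the partner period from 5 to 6 months, in line with Appendix 4 and criterion 9.
2. For female participants, state one collection period in both Section 8.3.5 and Appendix 4. If the 8-month test in footnote 16a is kept, make it 8 months in both, so that a pregnancy found at that test is collected. If the sponsor prefers 4 months, footnote 16a and its copy in SAP Appendix 2 must be revised as well.

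The cost is near zero: one number for partners and one for female participants, plus the footnote in two documents if 4 months is chosen. A clarification letter or the next amendment would do. The planned analyses do not change.
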